- 9. To gather some information on peri-partum risk factors for transmission (mode of delivery, maternal co-morbidities, colonising species)

We will explore appropriate ways to use this evidence, if deemed relevant, in the economic model.

Primary Endpoint

The primary aim of GBS2 is to evaluate whether the proportion of women prescribed IAP for prevention of vertical GBS transmission differs between screening strategy groups. In statistical terms, the null-hypothesis of no difference can be tested using a mixed logistic regression model with prescription of IAP as the dependent variable, study screening strategy group as the independent variable, and maternity unit as a grouping (random effect) variable. These models will be fitted using population averaged models (similar to multilevel models) using GEE methods in STATA. Population averaged models, as opposed to random effects models, will be used as within the framework of cluster randomised trials: random effects models both lack appropriate interpretation and might be biased. [52] Similar models will be fitted for secondary outcomes and appropriate link functions used for outcomes which are not binary. The primary outcome will be considered significant at the 5% level (and so 95% CIs reported).

Secondary Endpoint

Secondary outcomes will be interpreted cautiously as the CRT is not necessarily powered to detect a difference in these.

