5. METHODOLOGY

Centre eligibility

Maternity units will be eligible to participate in GBS2 if they are prepared to accept a policy of rapid test directed IAP administration as their standard practice of treating GBS colonisation for the duration of the study period. The Trusts hosting the maternity units will need to have microbiology facilities which are able to perform bacteriological culture.

Participant Inclusion Criteria

Presence of one or more of the following risk factors will define inclusion of the mother and baby into the study:

Version 1.0 22nd December 2015 GBS2 Page 17 of 81

- Previous baby with early or later onset neonatal GBS disease as reported by the mother and documented in the maternal notes
- GBS bacteriuria during current pregnancy, as documented in the maternal notes, irrelevant of whether the GBS bacteriuria was treated at the time of diagnosis with antibiotics
- GBS colonisation of the vagina and / or rectum (determined from a vaginal / rectal swab) in current pregnancy, as documented in the maternal notes
- Maternal pyrexia (>38°C) observed at any point in labour, or clinically suspected / confirmed chorioamnionitis
- Preterm labour (<37 weeks' gestation) with prelabour rupture of membranes of any duration
- Preterm labour (<37 weeks' gestation) if there is suspected or confirmed intrapartum rupture of membranes lasting more than 18 hours

The first three risk factors are apparent from the women's history and will be evident before the start of labour, enabling women to be immediately approached for a vaginal and rectal swab. Preterm labour with prelabour rupture of membranes will be evident at presentation in labour.

Pyrexia, chorioamnionitis and prolonged rupture of membranes in preterm labour are emerging risk factors associated with maternal GBS colonisation and labouring women should be monitored for these signs.

[figure not shown]
Exclusion Criteria

Women who will automatically be excluded from screening will be:

- Those under 16 years of age
- Women in labour at a gestation age of <24 weeks
- Women who, on arrival at the maternity unit, are already in second stage of labour or who are considered likely to deliver their baby imminently
- Women whose baby is known to have died in utero or who has a congenital anomaly incompatible with survival at birth
- Women having an elective Caesarean delivery

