All these exclusion criteria should be apparent when the woman arrives at the maternity unit labour ward or delivery suite.

The common eligibility criteria are shown in Figure 2 (below):

Study Design / Plan - Study Visits

The data flow for the main study is shown in Figure 3.

[figure not shown]
A paper checklist will be used by delivery suite midwives to screen all women presenting to the labour ward to record the presence or absence of maternal risk factors that determine eligibility. This eligibility checklist will simply implement the RCOG guidelines which are, or inform, the standard policy for GBS screening in most participating hospitals. This checklist will be inserted into maternal handheld notes for women delivering during the study period.

If the woman does have risk factors associated with GBS colonisation then the midwife will take a GBS2 Grab Bag. This is a Ziploc back which contains all the forms and consumables relevant to the site. All the items in this bag will be labelled with

the same unique trial number. The midwife will record this trial number alongside a number of identifiers such as the woman's name, NHS / Hospital number and Date of Birth on a central form held at the local site. Should risk factors not be present then the woman will be monitored during her labour for any emerging risk factors.

Figure 3: Data Flow Pathway (Main study)

The time of the start of labour, timing of the swab, test results, and any antibiotics received will be recorded alongside other factors. The checklists will be collected

centrally at the local site and compiled on a daily basis by a designated midwife. The trial forms will be completed as labour progresses and the woman gives birth. Personal identifiers will be recorded on any internal documents if demanded by Good Clinical or Good Laboratory practice, however these will not be made available to the trial team. Once the forms are completed then either a member of the local care team or the research midwife will transpose the information from the forms onto the secure trial database. Only the local trial number will be used to link the data together – no other patient identifiers will be entered on to the trial database. Paper copies of the data collection forms will be stored securely at the local site.

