The purpose of the obtaining the baseline current IAP usage rates is to stratify the randomisation of clusters. With a relatively small number of clusters it may be inappropriate to attempt to pair clusters. As clusters will be randomised in up to four waves, it is more appropriate to stratify the randomisation of clusters within each wave by baseline IAP rate. Maternity units will be randomised to follow either the risk factor based screening strategy or the rapid test strategy to direct the decision to offer IAP.

Version 1.0 22nd December 2015 GBS2 Page 31 of 81

Risk based screening units (i.e. those not assigned a rapid test system)

All women considered eligible for the study according to the risk factors for GBS transmission described should be offered IAP.

If a woman is pyrexic, or suspected or confirmed to have chorioamniotis, broad spectrum antibiotics (e.g. fourth generation cephalosporins) should be given immediately.

The use of IAP will be collected, including information of whether IAP was declined or deemed too late given the progression of the labour, along with the date and time the IAP was initiated.

Rapid test screening units

Supply of trial consumables

Units randomised to receive the rapid point of care test will be supplied with a Cepheid GeneXpert GBS rapid testing system plus a sufficient number of GeneXpert GBS test cartridges and other consumables to cover the number of women projected to have GBS risk factors presenting to their unit during the study period. Should stocks of consumables or test cartridges start to run low (to a level of around 25% of that initially supplied) then the centre should contact the Trials Office in Birmingham who will arrange re-supply.

Obtaining a vaginal-rectal swab

The use of the rapid test for screening will be restricted to women who present to the labour ward and who exhibit at least one of the risk factors associated with GBS colonisation.

Depending on the stage of labour the swabs will be obtained by either the woman herself, or a suitably qualified, trained, and locally approved member of the woman's care team. This could be on admission to the labour ward, before a vaginal examination is performed, or after a risk factor is detected - for example, maternal fever is observed.

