Each unit allocated to the rapid test screening policy will be required to locate the GeneXpert machine and computer centrally within the unit and have it plugged in and operational at all times. Immediately after the vaginal - rectal swab has been taken, one exposed swab head should be inserted into the GeneXpert GBS test cartridge. Should more than 15 minutes have elapsed from when the swab was inserted into the test cartridge to the test cartridge being loaded onto the machine and the analysis commenced then the test will be deemed to have failed and the woman should be administered prophylaxic antibiotics in compliance with RCOG guidelines. On the computer, the start test icon is selected, the NHS or hospital number entered alongside the patient's unique trial number. This trial number will be identical on each item of study material associated with this woman and her child. Once the start button has been clicked a blinking light on the machine will indicate which bay the cartridge should be loaded into. Once the door on the bay is shut, the test starts automatically. When the test is finished, the door opens and the result is displayed on the computer screen. Two printouts of the results will be available. To comply with Good Clinical Practice the first printout will contain identifiers to ensure that the patient receives the most appropriate treatment and results recorded in the correct set of notes. The second print out will show the unique number and the colonisation status and will be used for trial purposes.

It takes on average 35 minutes to give a result if GBS is present, 55 minutes to confirm if no GBS present, and an error message is presented if the test has failed.

If more than 48 hours have elapsed since the test result has become available and the woman has still to deliver then the test result shall be regarded as invalid. In this situation the woman should be re-swabbed and the presence of GBS tested for again using both the rapid test and microbiological techniques. This pathway is shown in the flow chart **in Figure 4**.

[figure not shown]

Figure 4: Example Patient Pathway (Centres assigned a rapid test)

Used test cartridges and swabs should be disposed of according to local policies for clinical waste.

The outcome of the rapid test will be recorded on the GBS2 checklist. Periodic downloads of the data held on the computer will supply data on the start time, duration and outcome of each test performed.

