Units supplied with a rapid test will be asked only to offer IAP based on the results of the rapid GBS test or if the woman specifically requests them, not the presence of maternal risk factors alone. If the rapid test is positive, the mother will be presumed to be colonised with GBS (given the anticipated high sensitivity) and offered IAP.

If the rapid test is negative, no IAP should be offered for prevention of GBS transmission, unless the women is pyrexic, suspected or confirmed to have chorioaminotitis, or directly requests antibiotic prophylaxis.

If more than 15 minutes have elapsed from when the swab was inserted into the test cartridge and the test cartridge being loaded onto the machine and analysis commenced, or the rapid test fails to deliver a result within 55 minutes of loading the sample on the machine the test will be designated as 'failed'. As the women has risk factors associated with GBS colonisation they will be given intrapartum antiobiotic prophylaxis as per the RCOG guideline. We do not anticipate that more than 10% of tests will fail to deliver a timely result.

Should more than 48 hours have elapsed since the test result has become available and the woman has still to deliver then the test result shall be regarded as invalid. In this situation the woman should be re-swabbed and the presence of GBS tested for using both the rapid test and microbiological techniques.

The use of any IAP will be collected, including information of whether IAP was declined or given the progression of the labour deemed too late to be administered. The date and time the administration of IAP was initiated will be recorded.

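### The exclusion of women thought likely to deliver imminently is an unblinded, post-allocation opinion, so the primary-outcome denominator can differ by arm

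*Protocol*

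**What the plan says.** Protocol section 5, Exclusion Criteria, removes women who on arrival "are already in second stage of labour or who are considered likely to deliver their baby imminently". The next sentence adds: "All these exclusion criteria should be apparent when the woman arrives at the maternity unit labour ward or delivery suite". Under Study Design / Plan, the people applying eligibility are the unit's own staff: "A paper checklist will be used by delivery suite midwives to screen all women presenting to the labour ward".

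Those staff know the allocation. Section 6 has the unit randomised and the result conveyed to the site before the study period is agreed. In section 5, rapid-test units must "locate the GeneXpert machine and computer centrally within the unit and have it plugged in and operational at all times".

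Women who are included can still turn out to be too late for treatment. The risk-factor arm collects "information of whether IAP was declined or deemed too late given the progression of the labour"; the rapid-test arm collects "whether IAP was declined or given the progression of the labour deemed too late to be administered". Such women remain in the trial.

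The primary question in section 4 is whether "the proportion of women prescribed IAP for prevention of vertical GBS transmission differs between screening strategy groups". The primary analysis is unadjusted, and the end-of-study electronic download covers only women who were included.

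**The concern.** A cluster trial that recruits after randomisation is protected only if the same kinds of women are counted in both arms. The protocol recognises this. Under the no-consent model it argues that all women with intrapartum risk factors must be counted, and it names selection by midwives, including unintentional selection under time pressure, as the bias to avoid. The imminent-delivery clause leaves room for that selection.

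The yardstick for what counts as imminent also differs by arm. A rapid-test unit has to take a swab, load a cartridge and wait on average 35 minutes for a positive or 55 minutes for a negative result. A risk-factor unit only has to offer prophylaxis. The same woman may therefore look too late to enter in one arm and not in the other, without any bad faith.

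Women close to birth are plausibly less likely to be prescribed prophylaxis. If they leave one arm's denominator and stay in the other's, the primary outcome moves with no effect of testing. Intention-to-treat analysis cannot restore women who were never counted.

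**Working it through.** **The plan's own figures.** Inputs from Statistical Considerations: 8 units per arm, 83 women per unit (664 per arm), control rate 75%, 90% power, 5% significance (taken as two-sided). Effective size per arm is 664/(1 + 82 × ICC): 364.8 at ICC 0.01 and 38.2 at ICC 0.2. Using unpooled variance and a noncentral t with 14 degrees of freedom:

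- 75% v 63%, ICC 0.01: power 90.7%.
- 75% v 38%, ICC 0.2: power 90.4%.

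The plan's detectable differences of 12 and 37 points reproduce.

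**Size of a denominator shift.** The protocol gives no number of late arrivals, so the following are assumptions. Let x be the share of at-risk women who are borderline, e the fraction of them excluded in one arm (none in the other), and b their prophylaxis rate. Let the rate with everyone counted be 75%. The excluding arm then reads

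(0.75 − x·e·b) / (1 − x·e).

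| Case | x = 5% | x = 10% |
|---|---|---|
| All excluded, none given IAP (e = 1, b = 0) | 0.75/0.95 = 78.9%, gap 3.9 | 0.75/0.90 = 83.3%, gap 8.3 |
| Half excluded, half the usual rate (e = 0.5, b = 0.375) | 0.7406/0.975 = 76.0%, gap 1.0 | 0.7313/0.95 = 77.0%, gap 2.0 |
| Retained women given IAP at the usual rate (b = 0.75) | gap 0 | gap 0 |

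Gaps are in percentage points.

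**Effect on the comparison, all-versus-none case.** Here 75% and the comparison rate apply to women who are not borderline, and borderline women get no IAP.

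- *Excluded in the rapid-test arm only.* The control arm reads 0.75(1 − x): 73.5%, 71.3% and 67.5% for x = 2%, 5% and 10%. Against 63% the difference shrinks from 12 to 10.5, 8.3 and 4.5 points, and power at ICC 0.01 falls from 90.7% to 81%, 60% and 22%. For 75% v 38% at ICC 0.2, power falls from 90.4% to 87%, 82% and 71%.
- *Excluded in the risk-factor arm only.* The 12-point reduction appears as 13.3, 15.2 and 18.3 points.
- *No true difference (75% in both).* The spurious gap is 1.5, 3.8 and 7.5 points. Type I error is 7%, 19% and 55% at ICC 0.01, and 5%, 6% and 10% at ICC 0.2.

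**The case against.** A reader might infer that the protocol treats one and the same situation in two contradictory ways. It does not. The exclusion is judged on arrival, whereas being too late arises as labour progresses. The latter category also has its own use, since pyrexia, chorioamnionitis and prolonged rupture can emerge late in a woman who arrived early. The two groups overlap at the margin, and no visible rule separates them there. That narrower point stands.

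A reader might also take the 4- and 8-point gaps as the expected bias. They need complete exclusion in one arm, none in the other, and no prophylaxis among the women kept. The last condition sits badly with the mechanism: if a control unit keeps a woman because a first dose still fits, she may well be prescribed it, and the gap shrinks towards zero. Second-stage women are already removed by an observable state, so x covers only the remainder.

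Nor do the documents support reading this as likely to manufacture a benefit. The suggested mechanism excludes more women in the rapid-test arm, which raises its rate and works against a reduction. The sponsor expects a large effect, and the 12-point benchmark belongs to the lowest ICC considered.

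Two uncertainties remain. The eligibility figure is not shown and may add detail. The wording that such women are excluded from screening could mean only that they are not tested. That ambiguity decides the denominator, so it needs resolving either way.

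**Conclusion.** The concern holds in a limited form. The text lets an unblinded opinion, formed after allocation, decide who enters the primary-outcome denominator. One arm has a practical reason to apply it more often, and the download of included women does not recover those left out. This runs against the protocol's own reasoning on midwife selection.

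The likelier direction is a higher apparent prophylaxis rate in the rapid-test arm, masking a true reduction; the reverse is possible. That staff will apply the clause differently is a risk, not something the document shows.

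The size cannot be known from the protocol. On a 75% rate, the upper bound is about 4 points (x = 5%) or 8 points (x = 10%), and about 1 to 2 points under the milder assumptions. This is material against the 12-point difference at ICC 0.01 and small against the 37-point difference at ICC 0.2. It is worth correcting but does not invalidate the design.

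**What to change.** In Exclusion Criteria and on the eligibility checklist, let only states recorded on arrival, such as second stage, remove a woman from the trial. Take the imminent-delivery opinion out of the rule that sets the primary-analysis denominator. State that women with a risk factor who are judged too close to birth to be swabbed or treated stay in the denominator of both arms under the existing too-late category, whether or not they were swabbed. They would then have a trial number and fall within the data download. Whether to swab remains a clinical decision; the change concerns only who is counted.

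The cost is a small edit to the eligibility text and checklist, data collection for a few unswabbed women, and slight dilution. If a share x receives no IAP in both arms, a 12-point difference becomes 12(1 − x): 11.4 points at x = 5% and 10.8 at x = 10%. Unswabbed women count towards the 1,340 but supply no test result, so they do not count towards the 676 needed for the accuracy study. Second stage is still assessed by unblinded staff, but it is a recorded finding and not a forecast.

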For women with prelabour rupture of membranes at term, including prolonged (>24 hours) rupture, the use of prophylactic antibiotics is not recommended. [48]

Current management protocols

Intrapartum antibiotic prophylaxis for maternal GBS colonisation

Where IAP is indicated for prophylaxis against GBS transmission, the standard treatment is the intravenous administration of three grams of benzylpencillin as soon as possible after the onset of labour, and half that dose at four hourly intervals until delivery, with equivalent doses of clindamycin for those allergic to penicillin. The RCOG suggests that to optimise the efficacy of IAP, the first dose should be given at least two hours before delivery, although a minimum of four hours is considered ideal. [49] Benzylpenicillin levels in cord blood appear to exceed the minimum inhibitory concentration for GBS as early as 1 hour after maternal administration, [50] but it is not known how this relates to prevention of transmission.

Management of neonates

Around 94% of neonates who develop EOGBS do so within 12 hours of delivery. Two thirds of these had mothers with one or more risk factors during labour, with a significant number exhibiting foetal distress and low Apgar scores at delivery.[31, 51] Where clinical signs and symptoms of sepsis are observed, the baby should be evaluated and antibiotics prescribed. Other infants without clinical signs but whose mother had risk factors should be observed closely in their first 24 hours after birth. Routine administration of antibiotics to babies deemed low risk is not recommended.

Rationale and Risks/Benefits

The women taking part in GBS2 in the control arm (units where usual practice is followed) will face no additional risks above that associated with standard practice. Women taking part in GBS2 in units where the rapid test is placed should quickly and confidentially know their GBS colonisation status. This has a number of benefits including:

- reducing antibiotic use by better identifying and only targeting those women colonised with GBS, Intrapartum antibiotics will only be given where they are needed
- reducing time spent in hospital by knowing the GBS colonisation status of the mother with considerable certainty, babies born to mothers with risk factors for, but who are not colonised with GBS can be discharged home sooner and with less medical intervention
- reducing readmissions Should a baby be born to a mother who has tested

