To reduce these factors as far as possible GBS2 will randomise at the level of the maternity unit. Each unit will be randomised to follow either their standard risk factor based strategy, or a strategy of administering IAP to women with risk factors associated with GBS colonisation based on the result of the rapid, point of care, PCR test.

Figure 4: An example patient pathway **Example Patient Pathway** CENTRES WITH RAPID TEST MACHINE START Flowchart "Is this Are an risk factors emerged? woman suitable for GBS2?" The woman is **NOT** eligible Maternal vaginal to take part in GBS2 & rectal swab Treat as per local policy Data Collection " GBS2 YES Eligibility / Test Result" RAPID TEST CARTRIDGE *If >15 mins has elapsed since > 15 mins since inoculated cartridge inoculation and it being BACTERIAL CULTURE cartridge on machine* YES loaded onto the test system then for GBS administer antibiotics to the woman Has > 48 hrs elapsed since the test? **Data Collection** Result "GBS2 Microbiology available within 55 mins form" YES Administer antibiotics YES to the woman YES Has labour in compliance with result positive guidelines for maternal GBS colonisation Has the voman requested antibiotics

Within cluster trials, it is important that all eligible participants are identified prior to the unit being randomised. As intrapartum risk factors can only be identified at the time when the screening strategy needs to be applied we need to include all women in this group. If consent was sought there would be selection by midwife (overtly or

Has labour

commenced?

Birth

Swab neonate's ear canal

as soon as convenient

after birth

YES

Has > 48 hrs elapsed since the test?

Data Collection "GBS2

Neonate / Discharge

form"

unintentionally, due to time pressures), and as a result of women declining to provide swabs or data for research. The selection bias caused by the need to approach and individually consent participants within a cluster leads to unreliable estimates of screening effectiveness.[53] However, if the screening strategy is adopted as standard practice by the maternity unit, and anonymous routinely collected data is retrieved, consent for research is unnecessary (although clinical consent for vaginal / rectal and neonatal swabs would prevail).

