Development of molecular methods that allow rapid bedside detection of microorganisms offers the potential to target antibiotic use more specifically than was previously possible. GBS1 showed that implementation of complex point of care (POC) tests is technically feasible. However the practical value of any POC test depends on accurate results being reliably available within a clinically relevant timeframe. To this end, careful consideration is required of a number of factors including the expected frequency of testing, achievable result turnaround times, the amount of hands-on test time, strategies to deal with test failure, and assurance of the ongoing availability of sufficient staff able to undertake testing when required.

The majority of the commercially available test systems require multiple preparation and incubation steps comparable to the previous generation Cepheid Smart-Cycler system. In light of the limitations found with this system in GBS1, the technology that we propose to investigate is the Cepheid GeneXpert system. The GBS Xpert test for this platform allows accurate detection of GBS within 35 minutes of placing an appropriate sample in the machine, with a hands-on preparation time of less than 2 minutes.

Existing research related to Cepheid GeneXpert GBS system

The Cepheid GeneXpert GBS system has been available since 2008 and several groups have assessed its accuracy in studies, although with different swabbing strategies and reference standard comparators. A systematic search of test evaluation studies and randomised comparisons of screening strategies using the Cepheid GeneXpert GBS system has been undertaken. Searches were made of Medline, Embase, Cochrane Clinical Trial Register, Cochrane Database of Systematic Reviews and the International Clinical Trial Registry Portal (ICTRP), from 2008 to the present (the GeneXpert GBS system received a CE mark in 2009) using search terms (group B streptococcus or streptococcus agalactiae) and (GeneXpert or pcr) and (identif\$ or screen\$ or diagnos\$ or test\$).

The search identified 15 test evaluation studies, from which data for meta-analysis could be extracted from 11 studies. There is one ongoing single centre study registered on ICTRP, at a UK private hospital, of which we were already aware. There were no randomised comparisons of strategies.

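### The 55-minute failure limit equals the stated average time to a negative result, leaving valid negatives no margin, and the protocol does not say whether a late negative seen before prophylaxis starts reverses the decision

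*Protocol*

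**What the plan says.** All references are to the protocol.

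- Section 5, GeneXpert rapid test platform, gives the run times: "It takes on average 35 minutes to give a result if GBS is present, 55 minutes to confirm if no GBS present". It adds that "an error message is presented if the test has failed", so the machine signals its own failures.
- Section 5, Antibiotic administration, adds a time rule: if "the rapid test fails to deliver a result within 55 minutes of loading the sample on the machine the test will be designated as" failed, the woman receives IAP under the RCOG guideline. Loading the cartridge more than 15 minutes after inoculation also counts as failure.
- The pathway in Figure 4 repeats the limit ("available within 55 mins").
- The same Antibiotic administration section instructs: "If the rapid test is negative, no IAP should be offered for prevention of GBS transmission", except for pyrexia, suspected or confirmed chorioamnionitis, or the woman's own request. It also states: "We do not anticipate that more than 10% of tests will fail to deliver a timely result".
- Section 10 describes the positive run time as a ceiling, not an average: the test "allows accurate detection of GBS within 35 minutes of placing an appropriate sample in the machine".

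**The concern.** The cut-off for calling a test failed is the same number as the stated mean time to a negative. Positives have 20 minutes in hand and negatives have none. The rule can therefore turn valid negatives into failures while hardly touching positives, and each woman affected is directed to the treatment that the test was meant to spare her.

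IAP prescription is the primary outcome of the cluster trial, so each such woman narrows the contrast between arms. This is not an estimation bias: the comparison would correctly measure the policy as run. The worry is that the policy would be weaker than intended because of a threshold and not because of the test.

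There is also a practical gap. Take a negative that appears at minute 57, before any antibiotic has been given. One instruction has already declared failure and called for IAP. Another says that a negative test means no IAP. The prose does not say which prevails.

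**Working it through.** **Margin.** Limit minus stated average: 55 − 35 = 20 minutes for positives and 55 − 55 = 0 for negatives.

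**Inputs** (Statistical considerations). GBS prevalence 29.8%; sensitivity 96.4%; specificity 98.9%; 8 units of 83 women per arm (664); control IAP 75% (planning rate) or 60% (second row of Table 2); ICC 0.01 to 0.2. Untimely tests: at most 10%.

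**How many negatives may be late under the 10% expectation.**
- P(test positive) = 0.298 × 0.964 + 0.702 × 0.011 = 0.295
- P(test negative) = 1 − 0.295 = 0.705
- Largest late share of negatives = 0.10 / 0.705 = 14.2%, or about 0.10 × 664 = 66 women, before any machine error or loading delay is counted
- If 5% of tests fail for other reasons, the share falls to (0.10 − 0.05) / (0.705 × 0.95) = 7.5%

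**Can a mean of 55 minutes sit with at most 14.2% above 55?** Take a lognormal run time as an illustration. P(X > mean) = 1 − Φ(σ/2) = 0.142 needs σ = 2.14, which puts the median at 55 × exp(−2.14²/2) = 5.5 minutes. That is not credible for this device. So if the 10% expectation holds, run times are nearly fixed, or 55 minutes is close to a maximum.

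**IAP in the rapid-test arm at the 10% ceiling** (every positive and every failed test assumed treated; exceptions for pyrexia or request ignored):
- all failures are late negatives: 0.295 + 0.10 = 39.5%
- the same 10% fail for reasons unrelated to GBS status: 0.29499 × 0.90 + 0.10 = 36.5%
- difference: about 3 percentage points

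**Power.** Design effect DE = 1 + 82 × ICC; SE = √{[p_c(1 − p_c) + p_r(1 − p_r)] × DE / 664}; noncentral t with 14 df, two-sided 5%. The method reproduces Table 2: at its detectable rates for 75% control (63, 55, 48 and 38% at ICC 0.01, 0.05, 0.1 and 0.2) it gives 91, 90, 90 and 90%, against the stated 90%.

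Worked case, control 75%, ICC 0.2: DE = 17.4. With 39.5%, SE = 0.106 and 0.355 / SE = 3.36, so power is 88%. With 36.5%, SE = 0.105 and 0.3845 / SE = 3.67, so power is 93%.

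| Control IAP | ICC | Ordinary failures (36.5%) | All late negatives (39.5%) |
|---|---|---|---|
| 75% | 0.1 | >99% | 99% |
| 75% | 0.2 | 93% | 88% |
| 60% | 0.05 | 95% | 88% |
| 60% | 0.1 | 77% | 65% |
| 60% | 0.2 | 50% | 40% |

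**The case against.** The strongest reply is that no harm to valid negatives is shown. The protocol gives no spread of run times, and section 10 treats 35 minutes as a ceiling. If 55 minutes is likewise the maximum, few or no valid negatives are lost and the only error is a loose phrase. That stands, and it is why the size is left open.

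The limit is also a clinical trade-off. Section 3 reports RCOG advice that "the first dose should be given at least two hours before delivery", so waiting longer has a price. This stands too, and it argues for a short margin. It does not argue for leaving the rule and the run time unreconciled.

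Four stronger readings might be inferred, and the documents do not support them.

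- *That the protocol is silent on tests running past the limit.* It is not: such a test is failed and IAP is given. Only the effect of a valid negative appearing afterwards is open. Figure 4 is legible here only in fragments, so the drawn pathway may deal with it; the prose does not.
- *That about a third of tests would fail.* If run times were symmetric about 55 minutes, half of negatives would be late: 0.5 × 0.705 = 35% of all tests, with IAP near 65%. No distribution is stated, and this one contradicts the protocol's own 10% expectation.
- *That the rule costs 10 points of IAP, from 29.5% to 39.5%.* The lower figure assumes no failed test at all, whereas the plan already accepts up to 10% untimely tests. The fair comparator is 36.5%.
- *That sensitivity and specificity would be distorted.* This needs late valid results to be left out of the accuracy table, which the protocol does not state. Duration and outcome are downloaded for every test, and the handling may be set in a statistical analysis plan that is not at hand.

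**Conclusion.** The point holds as a minor flaw in a bedside rule. The failure limit and the stated average time to a negative are the same number. Taken literally, that does not fit the 10% expectation, and the status of a valid negative arriving just after the limit but before IAP is not settled.

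Inside the 10% ceiling the added effect on IAP in the rapid-test arm is at most about 3 points (39.5% against 36.5%). At the 75% planning rate, power stays at 88% or more even at ICC 0.2, which the protocol calls very conservative. At 60% control it falls by 7 to 12 points for ICC 0.05 to 0.2. These are upper bounds: every failure is taken to be a late negative, and every failed test to lead to IAP. The effect would be larger only if more negatives ran late than the protocol expects. It is close to nil if 55 minutes is really the maximum run time.

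**What to change.** 1. In Antibiotic administration and Figure 4, state that a valid negative reported after the limit guides care if IAP has not yet started.
2. Reconcile the platform description with the failure rule. If 55 minutes is the maximum run time, correct the words *on average*. If it is an average, set the limit a few minutes above the device's longest normal negative run time, using run-time data that the protocol does not currently give.

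Both are wording changes and need no extra women, tests or data. The cost of a later limit is a few minutes' delay to fallback IAP for women whose test has truly failed. Given the two-hour target before delivery, the margin should be short.
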